3.3 General Considerations

Categorical variables will be summarized using frequency and percentages, where the denominator for calculation is the underlying analysis set population, unless otherwise stated. A row denoted as “Missing” will be included in the count tabulations where necessary to account for missing values. Summaries will be provided by treatment and visit when applicable.

Continuous variables may be summarized with descriptive statistics of number of participants with available data (n), mean, standard deviation (SD), median, the first quartile (Q1), third quartile (Q3), minimum and maximum. Summaries will be provided by treatment and visit when applicable.

For concentration data and log-transformed data, descriptive statistics (i.e., n and n < lower limit of quantification (LLOQ) [number of participants with available result and number of participants with results below the limit of quantification], geometric mean, geometric SD, arithmetic mean, SD, co-efficient of variation, median, min and max) will be presented by treatment group and visit, when applicable.

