4.2.3.4 Analysis of Exploratory Endpoints

4.2.3.4.1 SARS-CoV-2 RT-PCR-positive Symptomatic Illness

The incidence of SARS-CoV-2 RT-PCR-positive symptomatic illness will be summarized with descriptive statistics in the FAS at the final data readout only. The number and percentage of participants who have the events will be provided overall and before Day 183, or Day 365.

Participants will be included as an event if they have RT-PCR-confirmed SARS-CoV-2 prior to Day 183, or Day 365, after first IMP dose and present with at least one of the qualifying symptoms as defined in the CSP. A positive SARS-CoV-2 RT-PCR will be defined based on the central laboratory result whenever both central and local laboratory results are available for NP swabs, or if only a central lab NP swab result is available. If only a local NP swab laboratory result is available, then the local laboratory result will be used. If no SARS-CoV-2 RT-PCR results are available, the participant will be considered as not having a RT-PCR-positive symptomatic event. Data from the eCRF will be used to determine if the participant met the qualifying symptoms. If a participant's first case of SARS-CoV-2 RT-PCR positive symptomatic illness occurs on or after Day 183, or Day 365, the participant will be considered as not having an event, respectively. Death due to COVID-19 or hospitalization due to COVID-19 can contribute to this endpoint when a qualifying symptom assessment is not observed.

- For participants with an event after first IMP dose, before Day 183, or Day 365, the date of event will be defined as the earliest symptom onset date from those which triggered an illness visit, where COVID-19 was confirmed with a positive SARS-CoV-2 RT-PCR laboratory test. In the case of death due to COVID-19 or hospitalization due to COVID-19, the date of event is the earliest date of death/date of hospital admission when a qualifying symptom is not observed.

If any of the following censoring reasons are met, the censoring date will be defined as follows:

- Participants who had SARS-CoV-2 RT-PCR positive test prior to first IMP dose will be censored at date of first IMP dose.
- Participants who receive a COVID-19 vaccination after first IMP dose, and prior to having an event before Day 183, or Day 365 will be censored at the date of vaccination.

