- Participants who have a protocol deviation for receiving restricted medication after first IMP dose, and prior to having an event before Day 183, or Day 365 will be censored at the date of the deviation.
- Participants who have a record-level exclusionary protocol deviation for PK samples (see Table 5 in most recent version of PDMP) after first IMP dose, and prior to having an event before Day 183, or Day 365 will be censored at the date of the deviation.
- Participants who discontinue early from the study after first IMP dose, and prior to having an event before Day 183, or Day 365 will be censored at date of end of study or date of last assessment, whichever is later. For participants who continue to participate in the study at the time of the analysis, the data cut off (DCO) date will be used as their last assessment date. For participants with no post-baseline visit data available, the date of the first IMP administration will be used i.e., follow-up will be 1 day.

The follow up time will be calculated as the minimum of the date of censoring, date of event, and date of Day 183 or Day 365 – date of first IMP dose + 1. When the minimum of the date of censoring and date of Day 183 or Day 365 is prior to date of event, then participants will be censored at their defined end of follow up time. Otherwise, participants will be identified as having an event at this time.

Time to the first SARS-CoV-2 RT-PCR-positive symptomatic illness episode will be analyzed using Kaplan-Meier (KM) method and quartiles will be presented. Proportion of participants who experience event, participants who are censored, breakdown of events, and reasons for censoring will be presented by treatment group at Day 183 or Day 365. KM plot will also be generated by treatment groups.

A listing will be provided for all COVID-19 symptom assessments and NP swabs assessed by RT-PCR (both local laboratory and central laboratory samples) regardless of RT-PCR result.

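### Symptomatic COVID-19 incidence is tabulated only as a crude FAS percentage; the KM analysis gives quartiles and a plot but no cumulative incidence with CI at Day 183 or Day 365

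*SAP*

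**What the plan says.** SAP 4.2.3.4.1 states that the incidence of RT-PCR-positive symptomatic illness is "summarized with descriptive statistics in the FAS at the final data readout only". It adds: "The number and percentage of participants who have the events will be provided overall and before Day 183, or Day 365". The section names no denominator, so the default in SAP 3.3 applies: "where the denominator for calculation is the underlying analysis set population, unless otherwise stated". That is the whole FAS.

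The section then lists five grounds for censoring: a positive RT-PCR before the first dose, COVID-19 vaccination, a restricted-medication deviation, a deviation that excludes PK records, and early discontinuation from the study. The first takes effect at once: "Participants who had SARS-CoV-2 RT-PCR positive test prior to first IMP dose will be censored at date of first IMP dose". When the censoring date falls before the event date, the participant is treated as censored.

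Time to first illness "will be analyzed using Kaplan-Meier (KM) method and quartiles will be presented". Two further outputs follow. One is a table for the two cut-off days: "Proportion of participants who experience event, participants who are censored, breakdown of events, and reasons for censoring will be presented by treatment group". The other is a figure: "KM plot will also be generated by treatment groups".

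A separate rule covers missing tests: "If no SARS-CoV-2 RT-PCR results are available, the participant will be considered as not having a RT-PCR-positive symptomatic event". It affects the KM estimate as well as the percentage, and the change proposed here leaves it as it is.

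**The concern.** The plan defines follow-up and censoring with care, but the incidence figure a reader will take from the tables does not allow for shortened follow-up. A participant censored on Day 40 counts the same in the denominator as one followed event-free to Day 365. The percentage is therefore lower than the cumulative incidence whenever participants are censored while still at risk. Such censoring is foreseeable: Protocol 6.5.1 permits COVID-19 vaccination outside 14 days of any dose, and vaccination is a censoring event.

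The KM analysis does allow for censoring, but its one named numerical summary may be empty. Follow-up is cut at Day 183 or Day 365, and a quartile exists only if the curve reaches it by then. If it does not, the censoring-adjusted incidence can only be read off a plot, without a CI. The matching objective in SAP 1.1 is to estimate efficacy for prevention of COVID-19, and neither output gives a reportable estimate of 6- or 12-month incidence.

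**Working it through.** **Plan's own figure.** None exists for this endpoint. The only sample-size figure (SAP 1.3) concerns adverse events: 1 − 0.97^100 = 0.952, which agrees with the stated 95%. It does not bear on this point.

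**Inputs.** From the documents: 100 participants per arm (SAP 1.3), FAS denominator (SAP 3.3), and cut-offs at Day 183 and Day 365 (SAP 4.2.3.4.1). Assumed, because the documents give no values: true incidence I by Day 365 of 5% to 30%, and censoring probability C by Day 365 of 0% to 60%. Event and censoring hazards are taken as constant and independent. Events after the censoring date are not counted, as the follow-up-time paragraph of 4.2.3.4.1 directs.

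**Step 1: crude percentage.** Let λ = −ln(1 − I) and μ = −ln(1 − C), both per follow-up period. Then

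expected crude = λ/(λ + μ) × [1 − (1 − I)(1 − C)].

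For I = 10% and C = 40%: λ = 0.1054, μ = 0.5108, λ/(λ + μ) = 0.1710, and 1 − 0.90 × 0.60 = 0.46. Crude = 0.1710 × 0.46 = 7.9%, which is 21% below 10% in relative terms.

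| True incidence by Day 365 | C = 20% | C = 40% | C = 60% |
|---|---|---|---|
| 10% | 9.0% | 7.9% | 6.6% |
| 20% | 18.0% | 15.8% | 13.3% |
| 30% | 27.1% | 23.8% | 20.2% |

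In the first row the relative shortfalls are about 10%, 21% and 34%. In 3,000 simulated arms of 100 per scenario, the mean KM cumulative incidence at Day 365 was within 0.3 percentage points of the true value throughout.

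Censoring on Day 1 acts in direct proportion. If 10% of the FAS is censored then, a true 20% becomes 0.20 × 0.90 = 18%.

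**Step 2: can the quartiles be estimated?** The KM lower quartile is the first time at which S(t) ≤ 0.75, so KM cumulative incidence must reach 25%. The median needs 50% and the upper quartile 75%. The simulated chance that even the lower quartile is estimable by Day 365, over C = 0% to 60%, is:

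| True incidence | Chance lower quartile is estimable |
|---|---|
| 5–10% | 0% |
| 15% | 1–2% |
| 20% | 12–19% |
| 25% | 48–54% |
| 30% | 79–88% |

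Without censoring this is the binomial probability of at least 25 events in 100: 0.6%, 13.1%, 53.8% and 88.6% at 15%, 20%, 25% and 30%. The simulation at C = 0 gave 0.6%, 12.9%, 53.7% and 87.9%.

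**Step 3: which incidence sets the threshold?** It is the KM incidence, not the crude one. At true incidence 30% and C = 40%, 39% of simulated arms had a crude percentage below 25% and still an estimable lower quartile.

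**The case against.** The strongest reply is that the plan already discloses what is needed. The KM plot by arm shows the censoring-adjusted curve, and the table beside it gives the proportions censored, with reasons. A reader might infer that quartiles are the only KM output, or that the censoring rules feed no planned result. The documents contradict both: the rules determine event status, the quartiles, the plot and the censoring table. What remains is that no cumulative incidence value and no CI is tabulated.

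A reader might also infer that many participants are censored early, or that one arm is affected more than the other. Neither document gives a rate or suggests a difference. Study termination need not add much: under Protocol 1.3, participants last dosed at Day 183 have the Early Discontinuation visit in place of Day 365. At 20% censoring the shortfall is modest, for example 20% reported as 18.0%. At true incidence 15% and 40% censoring the crude figure is 11.8%. That is 3.2 points low, against a binomial standard error of √(0.15 × 0.85/100) = 3.6 points.

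KM is not assumption-free either. Censoring at vaccination, restricted medication or discontinuation may be informative, and then KM need not recover the true incidence. Protocol 9.4.3.1 asks only for descriptive statistics, which the crude percentage satisfies. These points stand. They support adding the KM figure with its caveat, not removing the percentage.

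**Conclusion.** The point holds as a reporting gap. The tabulated incidence is a crude FAS percentage in which censored participants count as event-free, and the only numerical KM statistic named cannot be estimated if KM cumulative incidence stays below 25% by the cut-off.

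The size depends on rates the documents do not give. The relative shortfalls of about 10%, 21% and 34% rest on a true incidence of 10%, on 20%, 40% and 60% censoring, on independent constant hazards, and on post-censoring events being left out of the count. It would go too far to say that the quartiles will all be inestimable: at a true incidence of 30% the lower quartile would usually be available.

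Severity is minor. Protocol 8.1 calls the efficacy assessments exploratory, no hypothesis is tested (SAP 3.3.4), both arms receive AZD7442, and the primary endpoints are safety and ADA.

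**What to change.** In SAP 4.2.3.4.1, keep the counts, percentages, quartiles, censoring table and KM plot. Add, by treatment arm, the KM cumulative incidence at Day 183 and at Day 365, each with a 95% CI on the log-log scale. Use these values wherever the report describes 6- or 12-month incidence, with a footnote that they assume non-informative censoring. One further sentence should say whether events after the censoring date enter the crude counts.

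The cost is a few lines of SAP text and one table shell. The KM fit already planned supplies the estimates, and no new data are needed.

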4.2.3.4.2 Post-treatment Response for SARS-CoV-2 Nucleocapsid Antibodies

The incidence of participants who have a post-treatment response (negative at baseline to positive at any time post-baseline) for SARS-CoV-2 nucleocapsid antibodies will be summarized using FAS by treatment group overall and before Day 183, or Day 365 at the final data readout only. Same censoring criteria as described in Section 4.2.3.4.1 will be applied.

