5.2 Exclusion Criteria

Participants are excluded from the study if any of the following criteria apply:

Medical Conditions

- 1 Any clinical signs and symptoms consistent with COVID-19, eg, fever, dry cough, dyspnea, sore throat, fatigue for ≥ 5 days or confirmed COVID-19 infection by appropriate laboratory test within 28 days prior to screening. Prior COVID-19 infection is not an exclusion.
- 2 History or current hospitalization for worsening disease during the one month prior to screening, with no change in condition at the time of study enrollment as judged by the Investigator.
- 3 Current need for hospitalization or immediate medical attention in a clinic or emergency room service in the clinical opinion of the Investigator.
- 4 Previous hypersensitivity, infusion-related reaction, or severe adverse reaction following administration of a mAb.
- 5 Known history of allergy to any component of the IMP formulation.
- 6 History of clinically significant bleeding disorder (eg, factor deficiency, coagulopathy, or platelet disorder), or prior history of significant bleeding or bruising following IV infusions or venepuncture.
- 7 Any other significant disease, disorder, or finding that may significantly increase the risk to the participant because of participation in the study, affect the ability of the participant to participate in the study, or impair interpretation of the study data.

- 8 Any co-morbidity requiring surgery within 7 days prior to study entry, or that is considered life-threatening in the opinion of the Investigator within 30 days prior to study entry.

Prior/Concomitant Therapy

- 9 Any prior receipt of investigational or licensed mAb or other biologic indicated for the prevention or treatment of SARS-CoV-2 or COVID-19 within 5 half-lives prior to screening or expected administration immediately after enrollment.
- 10 Have received a COVID-19 vaccination \leq 14 days before Day 1 or plan to receive a COVID-19 vaccination \leq 14 days after Day 1. (Such participants can subsequently be included in the study once they have reached $>$ 14 days after their last dose of vaccine).
- 11 Receipt of convalescent COVID-19 plasma treatment within 90 days prior to screening.

Prior/Concurrent Clinical Study Experience

- 12 Receipt of any IMP in the preceding 90 days or 5 half-lives, whichever is longer, or expected receipt of IMP during the period of study follow-up, or concurrent participation in another interventional study.

Other Exclusions

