8.5.2.2 SARS-CoV-2 Serology Assessments

Serum samples will be collected to assess SARS-CoV-2 antigen-specific antibody levels. Baseline serostatus and the rate of SARS-CoV-2 infection in participants receiving AZD7442 will be determined by seroconversion (negative to positive) in a validated SARS-CoV-2 N protein antigen assay operated by an authorized laboratory.

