3.2 Analysis Populations

Table 2: Populations for Analysis

Population/Analysis	Description
Enrolled	All participants who sign the ICF.
Full analysis set	All randomized participants who receive at least one dose of IMP. Participants will be assigned to their randomized treatment according to the intent-to-treat principle.
Safety analysis set	All participants who have received at least one dose of IMP. Participants will be assigned in this analysis set by the arm of treatment they actually received.
PK analysis set	All participants in the safety analysis set who received AZD7442 ¹ and who had at least one quantifiable serum PK observation post dose will be included in the PK analysis dataset. Participants will be assigned in this analysis set by the arm of treatment they actually received.
NLF PK analysis set	All participants in the safety analysis set who received AZD7442 ¹ and who had at least one quantifiable adjusted nasal lining fluid PK observation post dose will be included in the NLF PK analysis dataset. Participants will be assigned in this analysis set by the arm of treatment they actually received.
ADA evaluable analysis set	All participants in the safety analysis set who have a non-missing baseline AZD7442 ADA result and at least one non-missing post-baseline AZD7442 ADA result. This includes 2 separate evaluable analysis sets for AZD8895 and AZD1061. AZD7442 evaluable analysis set contains participants who are either AZD8895 evaluable or AZD1061 evaluable. Participants will be assigned in this analysis set by the arm of treatment they actually received.
nAb evaluable analysis set (Pseudovirus)	All participants in the safety analysis set who received AZD7442 ¹ , and who had at least one quantifiable serum observation (pseudovirus) post dose. Participants will be assigned in this analysis set by the arm of treatment they actually received.

Population/Analysis	Description
nAb evaluable analysis set (Authentic Virus)	All participants in the safety analysis set who received AZD7442 ¹ , and who had at least one quantifiable serum observation (authentic virus) post dose. Participants will be assigned in this analysis set by the arm of treatment they actually received.

Abbreviations: ICF, informed consent form; COVID-19, coronavirus disease 2019; IMP, investigational medicinal product.

¹As per participant-level exclusions from the analyses identified in the most recent version of the PDMP.

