4.1.6 Disease Characteristics

4.1.6.1 Definitions and Derivations

Disease characteristics include the following at baseline:

- Active treatment for solid tumor and hematologic malignancies (Yes/No);
- Receipt of solid-organ transplant and taking immunosuppressive therapy (Yes/No);
- Receipt of chimeric antigen receptor T-cell or hematopoietic stem cell transplant; moderate or severe primary immunodeficiency (Yes/No);
- Moderate or severe primary immunodeficiency (Yes/No);
- Advanced or untreated HIV infection (Yes/No);
- Active treatment with systemic high-dose corticosteroids, alkylating agents, antimetabolites, tumor necrosis factor blockers and other biologic agents that are immunosuppressive or immunomodulatory (Yes/No);
- Serum for SARS-CoV-2 Serology (Positive, Negative);
- Other (Yes/No)

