4.2.1.2 Derivations

The number and percentage of ADA-evaluable participants in the following ADA categories in each treatment group will be determined. The number of ADA-evaluable participants in the treatment group will be used as the denominator for percentage calculation. Note that, ADA responses will be summarized for AZD8895, AZD1061, and AZD7442 separately.

- ADA positive at any visit (at baseline and/or post-baseline). AZD7442 is ADA positive if either AZD8895 or AZD1061 is ADA positive. The percentage of these participants in a population is known as ADA prevalence.
- Treatment-induced ADA positive (ADA negative at baseline and ADA positive at ≥ 1 post-baseline assessment with ADA titer $\geq 2 \times$ MRD [minimum required dilution]). In a situation that one of the components AZD8895 and AZD1061 is treatment-induced ADA positive, and the other component is treatment-boosted

ADA positive (as defined below), AZD7442 will be counted in the worst case (i.e., treatment-induced ADA positive).

- Treatment-boosted ADA positive (baseline ADA titer that was boosted by ≥ 4 -fold following drug administration). AZD7442 is treatment-boosted ADA positive if either AZD8895 or AZD1061 is treatment-boosted ADA positive, except in the situation described in the treatment-induced bullet above.
- Treatment-emergent ADA positive (either treatment-induced ADA positive or treatment-boosted ADA positive). The percentage of these participants in a population is known as ADA incidence.
- ADA positive post-baseline and positive at baseline.
- ADA positive at baseline and not detected post-baseline.
- Treatment-emergent ADA (TE-ADA) persistently positive for AZD8895 and AZD1061, is defined as treatment-emergent ADA positive participants having at least 2 post-baseline ADA positive measurements with titer $\geq 2 \times \text{MRD}$ at least 16 weeks (112 days) between the first and last positive measurement, or an ADA positive result at the last available assessment. AZD7442 is persistently positive if one of AZD8895 and AZD1061 is persistently positive.

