4.2.3.3 Handling of Dropouts and Missing Data

Unless otherwise specified, missing data will not be imputed. NLF PK analyses will be based on participants with data available. However, the following imputation methods will be used for descriptive analyses of NLF PK.

NLF PK data

Individual concentrations that are <LLOQ will be reported as <LLOQ in the listings for AZD8895 and AZD1061. Value of LLOQ will be used for both raw and adjusted AZD8895 and AZD1061 concentrations in summaries of AZD8895 and AZD1061 concentrations. AZD7442 concentration is sum of AZD8895 and AZD1061 concentrations, calculated after setting <LLOQ to LLOQ. Adjusted AZD7442 concentration is same as raw AZD7442 concentration in such cases.

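### SAP 4.2.3.4.2 sets no denominator for nucleocapsid seroconversion, so by default baseline-seropositive participants, who cannot be events, dilute the percentage

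*SAP*

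**What the plan says.** SAP 4.2.3.4.2 counts participants who move from "negative at baseline to positive at any time post-baseline) for SARS-CoV-2 nucleocapsid antibodies will be summarized using FAS by treatment group overall", and also before Day 183 and before Day 365. It borrows the censoring criteria of SAP 4.2.3.4.1 and names no denominator of its own.

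The default is in SAP 3.3: "Categorical variables will be summarized using frequency and percentages, where the denominator for calculation is the underlying analysis set population, unless otherwise stated". The FAS in SAP 3.2 is "All randomized participants who receive at least one dose of IMP", with no condition on serostatus or on available samples. Protocol 5.2 states that "Prior COVID-19 infection is not an exclusion". Baseline serostatus is tabulated by arm under SAP 4.1.6 as "Serum for SARS-CoV-2 Serology (Positive, Negative".

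On purpose, Protocol 8.5.2.2 says that "the rate of SARS-CoV-2 infection in participants receiving AZD7442 will be determined by seroconversion (negative to positive". On missing data, SAP 4.2.3.3 says "Unless otherwise specified, missing data will not be imputed". SAP 4.2.3.5 and 4.2.3.6 plan no sensitivity or subgroup analysis of the exploratory endpoints.

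**The concern.** The numerator needs a negative baseline result, but the default denominator does not. A participant who enters with nucleocapsid antibodies is counted in the percentage and cannot become an event, whatever happens later. The protocol treats seroconversion as the measure of the infection rate. The planned percentage therefore mixes two things: how often seronegative participants were infected, and how many participants were seronegative at the start. A reader who takes it as an infection rate among people at risk would read it too low.

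Nothing else in the plan separates the two. The pre-dose rule borrowed from SAP 4.2.3.4.1 rests on a positive RT-PCR and sets only a censoring date, so it removes nobody from the FAS. No planned analysis is restricted to baseline-negative participants.

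**Working it through.** The documents give no figure for seroconversion, so there is none to reproduce. The only sample-size figure, a 95% chance of at least one AE in 100 participants at a 3% rate, is correct (1 − 0.97^100 = 0.952) but does not bear on this point.

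**Inputs.** From SAP 1.3: 100 participants per arm. Assumed, because the documents do not give them: s, the share seropositive at baseline; r, the seroconversion rate in baseline-seronegative participants; and r2, the reinfection rate in baseline-seropositive participants. For simplicity all participants are taken as dosed, uncensored and with complete serology.

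**Step 1: the reported percentage.** Events = 100 × (1 − s) × r. Dividing by 100 gives r(1 − s). Dividing by the 100 × (1 − s) seronegative participants gives r. With r = 20% (exact 95% intervals are added here to show precision; SAP 4.2.3.4.2 plans none):

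| s | Whole FAS | Baseline-seronegative |
|---|---|---|
| 10% | 18/100 = 18.0% (11.0 to 26.9) | 18/90 = 20.0% (12.3 to 29.8) |
| 30% | 14/100 = 14.0% (7.9 to 22.4) | 14/70 = 20.0% (11.4 to 31.3) |
| 50% | 10/100 = 10.0% (4.9 to 17.6) | 10/50 = 20.0% (10.0 to 33.7) |

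The factor (1 − s) is the same at any r. At s = 10%, 30% and 50%, the whole-FAS figure is 9%, 7% and 5% if r = 10%, and 27%, 21% and 15% if r = 30%.

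**Step 2: infection in all dosed participants.** This is r(1 − s) + r2 × s. At r = 20% and s = 30%:

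- r2 = 0: 14.0% + 0 = 14.0%
- r2 = 10%: 14.0% + 3.0% = 17.0%
- r2 = 20%: 14.0% + 6.0% = 20.0%

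The whole-FAS figure matches all-dosed infection only when r2 = 0. This endpoint cannot show whether that holds, because a baseline-positive participant has no way to register an infection. When r2 lies between 0 and r, the whole-FAS and seronegative figures bracket the all-dosed rate.

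**Step 3: the arm difference.** With s = 30% and 100 per arm, the standard deviation of the chance difference in s between arms is sqrt(2 × 0.3 × 0.7/100) = 0.065, or 6.5 points. If r is 20% in both arms, a one-SD imbalance moves the difference in whole-FAS percentages by 0.20 × 6.5 = 1.3 points.

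**The case against.** The strongest reply is that the whole-FAS percentage is a legitimate quantity. Protocol 8.5.2.2 speaks of participants receiving AZD7442, which is the dosed population, and the seronegative figure does not describe that population either. This stands. A reader might infer that the seronegative rate is the one correct answer and the FAS figure an error, but Step 2 shows that neither is the all-dosed infection rate unless something is assumed about reinfection. That supports reporting both.

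The whole-FAS percentage is also an inference. SAP 4.2.3.4.1 and 4.2.3.4.3 promise numbers and percentages in so many words, while 4.2.3.4.2 does not. The percentage comes from naming the FAS together with the SAP 3.3 default. It is the natural reading, and no other section overrides it.

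Much can be recovered from planned output: baseline serology by arm lets a reader divide the responder count by the number negative at baseline. That gives an approximation. It does not show how many had no post-baseline result, or were censored, in each period.

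Three stronger inferences are not supported:

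- **Missing serology counted as negative.** Such participants do stay in the default denominator. But SAP 4.2.3.3 does not impute, and SAP 3.3 allows a row for missing values, so nothing declares them non-events.
- **The ADA analysis as precedent for dropping baseline positives.** The ADA evaluable set requires baseline and post-baseline results, but the category "Treatment-induced ADA positive (ADA negative at baseline and ADA positive at" later visits is still a percentage of all ADA-evaluable participants, baseline positives included.
- **A distorted comparison of arms.** Serostatus of 30% against 50% would turn an equal 20% risk into 14% against 10%. At 100 per arm, though, a 20-point gap is about three standard deviations (sqrt(2 × 0.4 × 0.6/100) = 6.9 points), so randomization makes it unlikely.

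**Conclusion.** The point holds as a minor one. As written, SAP 4.2.3.4.2 with the SAP 3.3 default yields r(1 − s), which understates infection among baseline-seronegative participants by the factor (1 − s). It equals infection in all dosed participants only if nobody seropositive at baseline is reinfected. The algebra does not depend on assumptions, but the size does. At r = 20% the shortfall is 2, 6 or 10 percentage points for s = 10%, 30% or 50%, and the documents give neither r nor s. Little rests on it: the endpoint is exploratory and descriptive, no hypothesis is tested, and the arm difference would move by about 1.3 points for a one-SD imbalance at s = 30% and r = 20%.

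**What to change.** In SAP 4.2.3.4.2, for each period already planned (overall, before Day 183, before Day 365):

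- Add the number and percentage with seroconversion among FAS participants who have a negative baseline nucleocapsid result and at least one non-missing, uncensored post-baseline result in that period.
- Keep the whole-FAS figure beside it.
- Show by arm how many are left out as baseline positive, as baseline missing, or for want of such a post-baseline result.

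This costs a sentence of SAP wording and one extra set of rows per period, with no new data. The denominators are smaller and the estimates less precise. The added figure conditions on follow-up, which early termination shortens, and on not having been censored, for example at vaccination. It describes only baseline-seronegative participants, which is why the whole-FAS figure should stay.

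Which scheduled sample closes each period, and how an event dated exactly on Day 183 or Day 365 is counted (SAP 4.2.3.4.1 is not consistent on this), are separate questions that this change does not settle.
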